### Study Protocol

The primary aim of this *in vivo* clinical study is to evaluate the depigmenting effect of an active ingredient incorporated into a food supplement through the evaluation of the melanin variation parameter, assessed with the equipment Antera 3D (Miravex, Ireland), after 28 consecutive days of food supplement's once-daily intake, in comparison with the baseline and a placebo.

The secondary objective of this study is to evaluate *in vivo* the depigmenting effect of the same active ingredient incorporated into a food supplement through the evaluation of the melanin variation parameter, assessed with the equipment Antera 3D (Miravex, Ireland), after 56 and 84 consecutive days of food supplement's once-daily intake.

Other goals of this clinical study are to evaluate *in vivo* the effect of the same active ingredient incorporated into a food supplement, after 28, 56 and 84 consecutive days of a once-daily intake, in comparison with the baseline and a placebo (1) on skin whitening/brightening through the evaluation of the L\* parameter, assessed with the equipment Antera 3D (Miravex, Ireland), (2) on the skin colour homogeneity through the measurement of the ITA° (Individual Typology Angle) parameter, assessed with the equipment Colorimeter® CL400, (3) on the skin tone evenness through the measurement of the standard deviation of the skin colour, assessed with the equipment Colorimeter® CL400, (4) on the skin density of the dermis, measured with the equipment Episcan 20 MHz (Longport Inc, United States), (5) on skin hydration assessed through capacitance measurements with the equipment Corneometer® CM825, (6) on the skin firmness, skin overall elasticity and skin total deformation measured with the equipment Cutometer® SEM 575 (Courage+Khazaka electronic GmbH, Germany), and (7) on skin radiance through clinical evaluation performed by an expert.

It is also objective of this clinical study to evaluate (8) subjects' tolerance, acceptability, perception of efficacy and future use/purchase intention towards the food supplements by filling out a subjective evaluation questionnaire after 28, 56 and 84 consecutive days of food supplement's once-daily intake.

To perform this study, 110 female healthy subjects, with ages between 25 and 60 years old, presenting mild to moderate fine lines and wrinkles, mild to moderate skin spots and phototype III to V, according to the Fitzpatrick phototyping scale, are enrolled. The subjects are randomly divided in two groups, the test group, taking the active ingredient incorporated into a food supplement and the placebo group, taking the food supplement without the active ingredient.

A 2 weeks washout period is performed, if subject has taken any kind of supplements (Vitamins, antioxidants, nutraceuticals) before the beginning of the study. In this period subjects cannot use any kind of supplements.

Each subject shall take 1 capsule of the food supplement per day, with lunch, for 84 consecutive days.

### **Statistical Analysis Plan**

A descriptive statistical analysis of the skin depigmenting, skin whitening/brightening, skin density, skin hydration, skin firmness, skin overall elasticity, skin total deformation and skin radiance results are performed for each group at each evaluation time-point, including the calculation of mean, standard deviation, and graphic representations.

Normality tests (Shapiro-Wilk test) are performed in order to assure normal distribution of the objective data obtained.

If normal distribution of the data is verified:

- paired-sample t-tests are applied to compare the results obtained for each parameter before (t0) versus after 28 (t1), 56 (t2) and 84 (t3) days of each food supplement's intake;
- independent t-tests are applied to compare the differences to baseline obtained with the investigational product versus the ones obtained with the comparator product at each time-point of evaluation (t1, t2 and t3).

For non-normal distributions non-parametric tests are used:

- Wilcoxon-tests are applied to compare the results obtained for each parameter before (t0) versus after 28 (t1), 56 (t2) and 84 (t3) days of each food supplement's intake;
- Mann-Whitney tests are applied to compare the differences to baseline obtained with the investigational product versus the ones obtained with the comparator product at each time-point of evaluation (t1, t2 and t3).

The significance value is established at 0.05 and at a power of 0.95.

Descriptive statistics of the subjective evaluation is performed at each time-point of evaluation with the calculation of number and percentage of subjects responding to each answer option and the results presented in graphic representations.

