## Results

The most relevant results that can be concluded from this study are:

	Investigational product	Comparator product placebo
Skin depigmenting	The product showed a skin depigmenting effect after 84 days of products' intake, in comparison to the baseline. After 28 and 56 days of products' intake, no improvement was observed.	No improvement in the skin depigmenting was observed after 28, 56 and 84 days of products' intake, in comparison to the baseline.
	The investigational product has no effect on the skin depigmenting, in comparison to the placebo.	
	
 
– 28.00%, 52.08% and 61.22% of the subjects agreed to strongly agreed that their skin is with less hyperpigmentation spots 28, 56 and 84 days after the daily intake of the investigational product, respectively.
 
– 26.53%, 55.10% and 53.07% of the subjects agreed to strongly agreed that their skin is with less hyperpigmentation spots 28, 56 and 84 days after the daily intake of the placebo, respectively.
 
	
Skin whitening/brightening	The product demonstrated a skin whitening/lightening effect after 56 and 84 days of products' intake, in comparison to the baseline. After 28 days of products' intake, no improvement was observed.	The product demonstrated a skin whitening/lightening effect after 56 and 84 days of products' intake. After 28 days of products' intake, no improvement was observed.
	The investigational product has a skin whitening/brightening effect, in comparison to the placebo, after 84 days of products' intake.	
	
 
– 32.00%, 60.42% and 55.10% of the subjects agreed to strongly agreed that their skin had a luminous effect 28, 56 and 84 days after the daily intake of the investigational product, respectively.
 
– 32.65%, 51.02% and 57.14% of the subjects agreed to strongly agreed that their skin had a luminous effect 28, 56 and 84 days after the daily intake of the placebo, respectively.
 
	
Skin colour	The product revealed a skin tone lightening effect after 28, 56 and 84 consecutive days of products' intake, in comparison to the baseline.	The product revealed a skin tone lightening effect after 56 days of products' intake, in comparison to the baseline. After 28 and 84 days of products' intake, no improvement was observed.

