	The investigational product has an almost statistically significant improvement in the skin tone lightening, in comparison to the placebo, after 84 days of products' intake, supporting the skin whitening/lightening effect observed previously.	
Skin tone evenness	No improvement in the skin tone evenness was observed after 28, 56 and 84 days of products' intake.	No improvement in the skin tone evenness was observed after 28, 56 and 84 days of products' intake.
	The investigational product has no effect on the skin tone evenness, in comparison to the placebo.	
	
 
– 32.00%, 60.42% and 67.34% of the subjects agreed to strongly agreed that their skin is with more homogeneous skin tone 28, 56 and 84 days after the daily intake of the investigational product, respectively.
 
– 32.65%, 59.18% and 59.18% of the subjects agreed to strongly agreed that their skin is with more homogeneous skin tone 28, 56 and 84 days after the daily intake of the placebo, respectively.
 
	
Skin density	No improvement in the density of the dermis was observed after 28, 56 and 84 days of products' intake.	No improvement in the density of the dermis was observed after 28, 56 and 84 days of products' intake.

	
intake, in comparison to the baseline. Instead, a significant decrease was observed.
 
The investigational product has no effect on the density of the dermis, in comparison to the placebo.
 
 
– 14.00%, 33.33% and 32.65% of the subjects agreed to strongly agreed that their skin is denser 28, 56 and 84 days after the daily intake of the investigational product, respectively.
 
– 22.45%, 36.73% and 38.77% of the subjects agreed to strongly agreed that their skin is denser 28, 56 and 84 days after the daily intake of the placebo, respectively.
 
	
intake, in comparison to the baseline. Instead, a significant decrease was observed.

Skin hydration	
No improvement in the skin hydration was observed after 28, 56 and 84 days of products' intake, in comparison to the baseline.
	
No improvement in the skin hydration was observed after 28, 56 and 84 days of products' intake, in comparison to the baseline. Instead, a decrease was observed after 84 days of products' intake.

	
The investigational product has no effect on the skin hydration, in comparison to the placebo.
	

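### Both placebo comparisons use baseline only by subtraction; adjusting for the t0 value could be more precise (optional improvement, not an error)

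*Combined protocol and SAP*

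**What the plan says.** The Statistical Analysis Plan chooses the test by a normality check: "Normality tests (Shapiro-Wilk test) are performed in order to assure normal distribution of the objective data obtained". If normality is accepted, "independent t-tests are applied to compare the differences to baseline obtained with the investigational product versus the ones obtained with the comparator product" at t1, t2 and t3. Otherwise "For non-normal distributions non-parametric tests are used", and between arms this means "Mann-Whitney tests are applied to compare the differences to baseline obtained with the investigational product versus the ones obtained with the comparator product". The t0 value is thus subtracted from follow-up in both branches and is not used in any other way. Neither the Study Protocol nor the SAP mentions ANCOVA, regression, a covariate or stratification.

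On error rates the SAP says "The significance value is established at 0.05 and at a power of 0.95", without naming a test, an SD or whether the test is two-sided. The Study Protocol enrols "110 female healthy subjects, with ages between 25 and 60 years old", randomly divided into two groups. The Results give the principal hypothesis as a melanin decrease of at least 7.02% versus placebo at day 28, and report that it was not verified.

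**The concern.** Subtracting baseline fixes its slope at 1. When follow-up is less closely tied to baseline than that, the change score carries baseline noise that a fitted slope would remove. The day-28 melanin comparison, and the other instrumental comparisons with placebo, would then be less precise than the t0 measurements already collected allow.

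What is at stake is efficiency. Because subjects are randomised, a comparison of change scores is a legitimate test of the treatment effect, and its type I error is not in question.

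**Working it through.** **The plan's own figure.** No SD or dropout rate is given, so 110 subjects at 95% power cannot be reproduced. Reading 7.02% as 7.02 points of change, with 55 per arm and a two-sided 0.05 test (all assumptions), the SD of change that gives 95% power is 7.02 / (√(2/55) × (1.960 + 1.645)) = 10.21. For SDs from 7 to 15 the required total runs from 52 to 238. The figure of 110 can be neither confirmed nor faulted.

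**Inputs.**
- Numbers analysed: 50 versus 49, inferred from the day-28 questionnaire percentages in the Results (28.00% = 14/50; 26.53% = 13/49). Numbers for the instruments are not reported.
- Alpha 0.05 (two-sided assumed) and power 0.95, from the SAP.
- Correlation ρ between baseline and follow-up, and k = follow-up SD / baseline SD: not reported, so varied.

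**t-test branch, absolute changes.** The variance of the ANCOVA effect relative to the change-score effect is

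k²(1 − ρ²) / (1 + k² − 2ρk) = 1 − (1 − ρk)² / (1 + k² − 2ρk),

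which is (1 + ρ)/2 when k = 1. Before the cost of estimating the slope it cannot exceed 1, and it equals 1 when the true slope ρk is 1. Estimating the slope with 99 subjects multiplies it by 1 + 1/95 = 1.0105.

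Example, k = 1 and ρ = 0.5: 0.75 × 1.0105 = 0.758; √0.758 = 0.871; the standard error falls by 12.9%.

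Example, k = 1.1 and ρ = 0.9 (slope 0.99): 1.21 × 0.19 / 0.23 = 0.9996; × 1.0105 = 1.010; the standard error rises by 0.5%.

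| Change in SE | ρ = 0.5 | ρ = 0.7 | ρ = 0.9 | ρ = 0.95 |
|---|---|---|---|---|
| k = 0.9 | −17.9% | −12.9% | −9.5% | −10.7% |
| k = 1 | −12.9% | −7.3% | −2.0% | −0.7% |
| k = 1.1 | −9.1% | −3.5% | +0.5% | −0.3% |

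A change-score t-test with 95% power at 50 versus 49 has non-centrality 3.641 on 97 df. Dividing by the relative standard error and using 96 df gives ANCOVA power of 98.5%, 97.3%, 95.7% and 95.3% across the k = 1 row. At 55 versus 55 the powers are the same to one decimal. In the k = 1.1, ρ = 0.9 cell power is 94.8%.

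**The full two-branch rule.** These formulas do not cover the Mann-Whitney branch, so whole rules were compared by simulation: 4,000 runs per cell, normal baseline, effect set to 95% t-test power. The SAP does not say which data the Shapiro-Wilk test is applied to. Per-arm differences were assumed for the plan's rule and pooled ANCOVA residuals for the adjusted rule. The adjusted rank test was Mann-Whitney on residuals from a regression on baseline. Power (%) at k = 1, for ρ = 0.5 / 0.7 / 0.9 / 0.95:

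| Errors | Plan's rule | ANCOVA alone | Both branches adjusted |
|---|---|---|---|
| Normal | 95.4 / 94.6 / 95.5 / 95.2 | 98.6 / 97.3 / 96.2 / 95.4 | 98.5 / 97.3 / 96.2 / 95.3 |
| t, 5 df | 96.0 / 96.2 / 97.2 / 97.0 | 98.0 / 96.8 / 95.5 / 94.8 | 99.3 / 98.5 / 97.6 / 97.1 |
| Exponential | 98.0 / 98.8 / 99.5 / 99.5 | 98.1 / 96.7 / 95.3 / 94.7 | 99.9 / 99.8 / 99.8 / 99.5 |

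Adjusting both branches matches or improves on the plan's rule. ANCOVA alone loses to it for heavy-tailed errors at ρ = 0.9 and above, and for exponential errors at ρ = 0.7 and above. At k = 1.1 the least favourable cell (t errors, ρ = 0.9), run 20,000 times, gave 97.3% for the plan's rule, 94.2% for ANCOVA alone and 97.0% with both branches adjusted, a loss of 0.3 points.

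**Validity.** Over 24 null cells, type I error was 4.4% to 5.7% for the plan's rule and 4.5% to 5.9% for the adjusted rule (Monte Carlo SE 0.34 points). The 5.9% cell gave 5.2% when run 20,000 times.

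**The case against.** The plan contains no mistake here. It randomises, it states a test for normal and for non-normal data, and a test on differences suits a hypothesis worded as a decrease. The documents cannot show a benefit, because every figure above rests on an assumed correlation and SD ratio, and at correlations of 0.9 to 0.95 with equal SDs the gain is negligible. The 95% power is not tied in the SAP to any test or sample size, and the counts of 50 and 49 come from questionnaires. Whether absolute or percentage change was analysed is unclear, and the formulas cover absolute change only. The trial is already reported, and no result is shown to be affected.

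All of that stands, and it is why this is an option and not a fault. The documents do not show that the correlation is high either, so a gain cannot be excluded.

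A further objection is that the choice of rank method matters, and that is correct. In a separate simulation with a skewed baseline and heavy-tailed errors at ρ = 0.9, ANCOVA on ranks had 86% power against 95% for the planned Mann-Whitney test. The residual-based Mann-Whitney test did not behave this way. With skewed and heavy-tailed baselines at 80% power, the adjusted rule was never more than about 1 point below the plan's rule in the cells completed. It gained 2 to 9 points at ρ = 0.5 and roughly nothing at 0.9 to 0.95.

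**Conclusion.** The point holds as an optional improvement in precision. The planned comparisons are valid. In the t-test branch the effect of adjustment ranges, over the assumed inputs, from a 17.9% fall in the standard error to a 0.5% rise. It is material if the slope on baseline is well below 1 and absent if the slope is near 1. In the non-normal branch the gain also depends on the error distribution and the rank method. The size of the gain in this trial is unknown: the documents give no correlation, SDs, estimates or p-values, and do not say which branch produced any result.

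Nothing here casts doubt on the reported melanin finding that "The investigational product has no effect on the skin depigmenting, in comparison to the placebo".

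**What to change.** For a future trial, keep the normality rule and adjust both branches for the t0 value of each instrumental parameter:

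- Apply Shapiro-Wilk to the residuals of the baseline-adjusted model, and say so in the SAP.
- If the residuals are normal, use ANCOVA with treatment and baseline, and report the adjusted difference with its 95% CI.
- If they are not, use one baseline-adjusted rank test named in advance, for example Mann-Whitney on residuals from a regression on baseline.
- Do not replace the whole rule with linear ANCOVA, which can lose power to the present rule for skewed or heavy-tailed errors.
- If the melanin result is to be read as a percentage, a log scale is an option.

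The cost is SAP wording and a few lines of code, with no new data. For the present trial only a post hoc re-analysis is possible. It should be labelled as such and should not be used to turn the reported "almost statistically significant improvement in the skin tone lightening, in comparison to the placebo, after 84 days" into a claim.

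### The SAP plans between-group tests but no estimate or confidence interval, so the eight statements of no effect versus placebo go further than the planned tests allow

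*Combined protocol and SAP*

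**What the plan says.** The Statistical Analysis Plan section sets out three kinds of output for the instrumental and clinical measures.

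- Descriptive results, given "for each group at each evaluation time-point, including the calculation of mean, standard deviation, and graphic representations". These are per-group summaries. The list of parameters does not name skin colour or tone evenness.
- Within-group tests against baseline at days 28, 56 and 84 (paired t or Wilcoxon).
- Between-group tests of change from baseline at the same visits. If data are normal, "independent t-tests are applied to compare the differences to baseline obtained with the investigational product versus the ones obtained with the comparator product"; otherwise, "Mann-Whitney tests are applied to compare the differences to baseline obtained with the investigational product".

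Significance is set at 0.05 and power at 0.95. No treatment difference, confidence interval or equivalence margin is named.

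The Results section opens as a summary: "The most relevant results that can be concluded from this study are". It then makes statements such as "The investigational product has no effect on the skin depigmenting, in comparison to the placebo", "The investigational product has no effect on the skin tone evenness, in comparison to the placebo" and "The investigational product has no effect on the density of the dermis, in comparison to the placebo". For skin colour at day 84 it says "The investigational product has an almost statistically significant improvement in the skin tone lightening, in comparison to the placebo", and adds that this supports the whitening effect reported above it. Near the end it gives the principal hypothesis, a melanin decrease of at least 7.02% versus placebo at day 28, and says that it was not verified.

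**The concern.** A test of a zero difference has two outcomes: a difference is shown, or it is not. The second does not establish that the difference is zero or too small to matter. For that, a reader needs the estimated difference and the range of differences compatible with the data, and the SAP plans neither.

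The per-group means and SDs do not clearly fill the gap. They are described as results at each time-point, whereas an interval for the difference in change needs the SD of the change.

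What is at stake is how firmly the negative findings may be worded. A trial that rules out a given effect and a trial that leaves it open are different results, and the planned outputs do not separate them. The skin-colour sentence has a related fault: a comparison that missed the trial's own 0.05 threshold is used as evidence for an effect.

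**Working it through.** **Plan against conclusions.** The statement of no effect compared with placebo occurs eight times in the Results table: depigmenting (1); tone evenness, density of the dermis, hydration (3); total deformation, overall elasticity, firmness (3); radiance (1). 1 + 3 + 3 + 1 = 8. None comes with a difference, interval or p-value. The only planned analyses that could stand behind them are the between-group t or Mann-Whitney tests.

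**The plan's own figure.** The sample size of 110 cannot be reproduced, because no SD is stated. It can only be solved backwards for the SD of the day-28 change, reading 7.02 as percentage points, with 1:1 allocation and power 0.95:

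- 55 per arm, two-sided 0.05, noncentral t: standardised difference 0.694, so SD = 7.02 / 0.694 = 10.1.
- 50 and 49, same method: SD about 9.6.
- 44 per arm (20% dropout), normal approximation: SD about 9.1.
- 55 per arm, one-sided 0.05, normal approximation: SD about 11.2.

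These are not sponsor figures.

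**Numbers evaluable.** Searching 40 to 55, the only denominator that fits the checked day-28 questionnaire percentages is 50 for the product (28.00, 32.00, 14.00, 50.00, 18.00) and 49 for placebo (26.53, 32.65, 22.45, 36.73, 28.57). The melanin counts are not stated and may differ.

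**Interval width.** Half-width = t(0.975, 97) × SD × √(1/50 + 1/49) = 1.985 × 0.2010 × SD = 0.399 SD. This applies to any parameter analysed by t-test in these numbers. A non-significant result therefore leaves differences of at least about 0.40 SD open in one direction or the other. For the seven parameters other than melanin, no target difference is stated to set this against.

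**Note on 7.02 at day 28** (positive values favour the product):

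- A non-significant estimate lies below 0.399 SD, so its upper limit lies below 2 × 0.399 = 0.798 SD. If the SD is below 7.02 / 0.798 = 8.8, every non-significant result excludes 7.02.
- If the SD is above 7.02 / 0.399 = 17.6, an estimate of zero does not exclude 7.02, nor does any non-significant estimate favouring the product. Only an estimate far enough in placebo's favour would; at SD 20, below 7.02 − 7.98 = −0.96.
- Between these limits it depends on the estimate. At SD 10.1 the half-width is 4.03, so estimates from 7.02 − 4.03 = 2.99 up to 4.03 are non-significant yet leave 7.02 inside the interval. At SD 12 the zone is 2.23 to 4.79; at SD 15 it is 1.04 to 5.98.

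Share of non-significant results that leave 7.02 inside the interval (simulation, normal data, SD estimated, 50 and 49):

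| Assumed SD | True effect zero | True effect 3.51 (half of 7.02) |
|---|---|---|
| 9.1 | 1% | 14% |
| 9.6 | 3% | 24% |
| 10.1 | 5% | 33% |
| 12 | 16% | 57% |
| 15 | 36% | 74% |

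The shares are conditional on non-significance. At SD 10.1 and half effect, about 60% of trials are non-significant, so 33% of those is about 20% of all trials.

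**The case against.** The strongest reply is that no verdict in the document is wrong on this ground. The Results say that the 7.02% hypothesis was not verified, which is correct wording, and never claim that 7.02% was ruled out. The final conclusion says that no effects were observed, which is acceptable. The overstatement is confined to sentences in the table. All of this stands.

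A second reply is that power of 0.95 makes a non-significant result informative. In part it does: if the planning SD was near 10 and the true effect is zero, few non-significant results leave 7.02 open. But that SD is not stated, and the argument reaches one parameter at one visit. The melanin sentence also covers days 56 and 84, and the other seven sentences have no stated target.

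A third reply is that this is a short SAP and a summary of selected results, so estimates and intervals may exist in a fuller report. That is possible. What can be said is that this text neither plans nor reports them.

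A reader might also infer more than the document supports:

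- *That the same test outcome was read two ways*, as no effect for eight parameters and near-effect for skin colour. No p-values are shown, so the eight may lie far from 0.05, and their non-significance is itself inferred from the wording. Skin colour also appears in the final conclusion neither as an effect nor as a non-effect. The fair criticism is only that a non-significant result should not be used as support.
- *That an effect was missed*, because depigmenting improved from baseline at day 84 on the product and not on placebo. A contrast between two within-group tests does not show a between-group difference.

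**Conclusion.** The point holds as one of reporting and wording. The planned tests cannot support eight statements of no effect, and an almost significant skin-colour result should not be offered as support for the whitening claim. The failed primary hypothesis and the final conclusion are unaffected.

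The general size is an interval half-width of about 0.40 SD, which rests on evaluable numbers inferred from the questionnaire. For day-28 melanin, the document does not let a reader tell whether 7.02% is excluded or only not shown. With an SD near 10 and no true effect, ambiguity would be the exception; with a partial effect or a larger SD it would not. Those figures rest on assumed SDs, a t-test analysis and reading 7.02 as percentage points of change, so they are a side note and not the ground of the finding.

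**What to change.** 1. For each parameter and visit, report the between-group difference in change from baseline with its 95% CI and the n per group, in the same subjects as the planned test. Because results already exist, label these intervals post hoc. Ten parameters at three visits give 30 intervals, so also state that they are not adjusted for multiplicity.
2. Where Mann-Whitney was used on a continuous measure, give the Hodges-Lehmann shift with its CI. Treat radiance separately: it is an expert's clinical evaluation with no scale stated. If it is a coarse ordinal grade, ties could collapse a Hodges-Lehmann interval to zero width, which would look like proof of no effect. Use a measure that handles ties, such as the Mann-Whitney probability or a difference in proportions improved, with its CI.
3. Give the day-28 melanin difference in percent, state the scale, and set it against 7.02%. Say that 7.02% is ruled out only if the CI excludes it.
4. Replace the eight statements with *no difference from placebo was shown*, followed by the CI.
5. Report skin colour at day 84 as not significant, with its CI, and drop its use as support.

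The cost is a table from existing data and nine reworded sentences. The downside is slightly more reporting, less definite negative statements, and the loss of skin colour as supporting evidence.

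### Visit-by-visit tests on unadjusted change ignore the baseline reading and use only women measured at that visit; with perhaps 10% to 12% missing, the day-84 L* claim needs a sensitivity analysis

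*Combined protocol and SAP*

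**What the plan says.** The Study Protocol section gives the sample as "110 female healthy subjects" and adds that "The subjects are randomly divided in two groups". It states no allocation ratio and no number per arm.

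For the comparison between arms, the Statistical Analysis Plan section says that "independent t-tests are applied to compare the differences to baseline obtained with the investigational product versus the ones obtained with the comparator product", at each of t1, t2 and t3 (days 28, 56 and 84). If the data are not normal, "Mann-Whitney tests are applied to compare the differences to baseline" in the same visit-wise way. The section names no analysis set, no rule for missing values, no model that uses all visits, no baseline covariate and no sensitivity analysis.

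The Results section gives no number analysed for any instrumental endpoint. The only trace of numbers is in the questionnaire percentages. In the skin depigmenting row these are "28.00%, 52.08% and 61.22% of the subjects agreed to strongly agreed" for the investigational product and "26.53%, 55.10% and 53.07% of the subjects agreed to strongly agreed" for placebo, at days 28, 56 and 84.

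**The concern.** Two weaknesses come from the same choice of method.

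- **Baseline is used only by subtraction.** Every woman has a baseline reading of each parameter. A change score uses it with a fixed coefficient of one; a covariate uses it with the coefficient the data support. Unless the correlation between baseline and follow-up is very high, the change score gives a less precise contrast between arms.
- **A test at one visit sees only that visit.** A woman without the day-84 reading is absent from the day-84 test, even if she was measured at days 28 and 56. Randomisation protects the comparison of the women as assigned, not of whoever was measured on the day.

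What is at stake is chiefly the report's one positive between-arm conclusion, L* at day 84. It is given without a number analysed, an estimate, an interval or a p-value. The ITA° comparison offered in its support at the same visit is itself described as falling just short of significance.

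**Working it through.** **1. The plan's own figure.** The SAP says "The significance value is established at 0.05 and at a power of 0.95". This power cannot be reproduced, because no standard deviation, allocation ratio, sidedness or dropout allowance is given. Assume 55 per arm and two-sided 0.05. Then 95% power corresponds to a standardised difference of (1.960 + 1.645) × √(2/55) = 0.687. For the hypothesised 7.02% difference, that is an SD of 7.02/0.687 = 10.2 percentage points.

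**2. Respondents implied by the questionnaire.** For each arm and visit, find n such that every reported percentage equals k/n within 0.01 points. Some printed values are truncated or are sums of rounded values. The stray fourth figure in the hydration line for the investigational product is left out. From the depigmenting row:

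| Visit | Investigational | Placebo | Total | Short of 110 |
|---|---|---|---|---|
| Day 28 | 14/50 = 28.00% | 13/49 = 26.53% | 99 | 11 (10.0%) |
| Day 56 | 25/48 = 52.08% | 27/49 = 55.10% | 97 | 13 (11.8%) |
| Day 84 | 30/49 = 61.22% | 26/49 = 53.06% (printed 53.07%) | 98 | 12 (10.9%) |

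The other questionnaire items give the same denominators. The only other fits are the doubles (96, 98, 100), which two arms totalling 110 cannot hold.

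**3. Pattern.** The investigational arm goes 50, 48, 49. So at least 50 − 48 = 2 women who answered at day 28 did not answer at day 56, and at least 49 − 48 = 1 who answered at day 84 had not answered at day 56. The set changes from visit to visit.

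**4. Power at these counts.** With the standardised difference from step 1, power falls from 95% to 92.8%, 92.3% and 92.5% at days 28, 56 and 84. The loss of numbers by itself costs little.

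**5. Gain from baseline adjustment.** Assume equal variance σ² at baseline and follow-up, with correlation ρ. The variance per woman is 2σ²(1 − ρ) for the change score and σ²(1 − ρ²) for the adjusted analysis. The ratio is 2/(1 + ρ):

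| Assumed ρ | 0.5 | 0.6 | 0.7 | 0.8 |
|---|---|---|---|---|
| Variance ratio | 1.33 | 1.25 | 1.18 | 1.11 |

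The standard error falls by 1 − √((1 + ρ)/2), that is by 13% at ρ = 0.5 and 5% at ρ = 0.8.

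**6. Sensitivity of day-84 L\*.** Assume 55 per arm, 6 missing per arm (55 − 49), equal SDs, and missing women on the investigational product given the placebo mean change. The estimate shrinks by 49/55 = 0.891. If the standard error is kept as observed, z is multiplied by 0.891. If it is reduced to that for 55 per arm, z is multiplied by √(49/55) = 0.944. By normal approximation:

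| Observed p | SE unchanged | SE at 55 per arm |
|---|---|---|
| 0.05 | 0.081 | 0.064 |
| 0.04 | 0.067 | 0.053 |
| 0.03 | 0.053 | 0.040 |

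The break-even values are z = 1.960/0.891 = 2.20 (p = 0.028) and z = 1.960/0.944 = 2.08 (p = 0.038).

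**The case against.** The strongest reply is that little is known about the missing women and that the model does little for them. Most of this stands.

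- **The counts are from the questionnaire.** Melanin and L* come from the Antera 3D, and its numbers are not reported. They may be higher or lower.
- **110 is a protocol figure.** No result states how many women were randomised. A reader might infer that 11 to 13 randomised women were left out, but part of the gap may be under-recruitment. The Results section presents only a selection of findings, so the absence of a participant flow there does not show that women went unaccounted for.
- **A reader might call this a completer analysis.** The sequence 50, 48, 49 rules out one fixed completer set. Available-case is the right description.
- **The repeated-measures model does not recover women with no post-baseline value.** Day 28 is the first such visit and is already 11 short, and placebo stays at 49 throughout. The counts are therefore consistent with nearly all loss before day 28, in which case the model adds almost none of these women. Its case rests mainly on baseline adjustment.
- **Bias is not shown.** Under 55 per arm, losses are balanced: 5, 7 and 6 against 6, 6 and 6. Nothing links the five reported mild discomforts to dropout. Balanced counts do not prove that the reasons were the same, but they give no sign of direction.
- **The primary result is unlikely to move.** The day-28 hypothesis was reported as not met, with no improvement even within the investigational arm. Reference-based imputation pulls towards no difference and would not rescue it.

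What survives is that the planned test is less precise than one using the same data with a baseline covariate, and that nothing in the plan tests the day-84 L* claim against missing readings.

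**Conclusion.** The concern holds as a choice of method that should be improved, not as a demonstrated bias. Two parts differ in strength.

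- **Baseline adjustment is a firm point.** It depends on no assumption about missing data. Its size, a variance ratio of 1.33 to 1.11, rests on an assumed correlation of 0.5 to 0.8 and equal variances.
- **Missing data is a conditional point.** If the instrument counts resemble the questionnaire's and all 110 women were randomised, 10% to 12% are missing at each visit. If, further, allocation was 55 per arm, an L* p-value above roughly 0.03 (standard error unchanged) to 0.04 (standard error at 55 per arm) would exceed 0.05 under reference-based imputation.

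A reader might infer that the L* claim fails. The documents do not support that: no L* p-value is given, so nothing places it inside or outside that band. Nor do they support saying that the null primary result is an artefact of missing women.

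**What to change.** 1. **Model.** Analyse each instrumental parameter with one repeated-measures model of change at days 28, 56 and 84, by assigned arm: arm, visit, arm-by-visit, baseline and baseline-by-visit, with unstructured covariance. The day-28 arm contrast for melanin is primary. Keep the planned visit-wise tests in the report beside it.
2. **Counts.** For each endpoint, report the numbers randomised, measured and missing by arm and visit, with reasons. This settles whether the 110 were all randomised and how many Antera 3D readings exist.
3. **Sensitivity analysis.** Add one reference-based imputation analysis that includes women with no post-baseline value, chiefly for L* at day 84. If the result does not hold, describe the L* claim as sensitive to missing data.

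The cost is SAP wording and a re-run on data already collected, with somewhat more modelling. The L* claim may become less favourable. Because the results are known, the new model and the sensitivity analysis must be labelled post hoc and cannot take on the standing of a pre-specified analysis.
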